2.2. Study Design

This Phase 3b, multicenter, open-label study, with a single arm design, will be conducted at investigator sites in Europe. Approximately 150 healthy infants 3 months of age will be enrolled to a single vaccine group to receive Nimenrix (MenACWY-TT).

On Day 1 (Visit 1), participants will be assessed for eligibility (including medical history and meningococcal vaccine history). If eligible, participants will have blood drawn for immunogenicity assessments and will receive the first dose of Nimenrix. Participants will receive a second dose of Nimenrix at 12 months of age (Visit 3).

Participants will have blood drawn prior to vaccination at Visit 1 and Visit 3 and 1 month after each vaccination at Visit 2 and Visit 4. E-diaries will be used to collect local reaction and systemic event data for 7 days after each vaccination. AEs will be collected through 1 month after each vaccination. In addition, SAEs and NDCMCs will be collected through the study from Visit 1 through Visit 4.

PFIZER CONFIDENTIAL	
Page 11	

In the case of extreme circumstances, such as natural disasters or a pandemic, visits for follow-up or procedures may need to be conducted through other means (eg, telephone, home visits).

PFIZER CONFIDENTIAL
Page 12

2.3. Schedule of Activities (SoA)

The SoA table provides an overview of the protocol visits and procedures. Refer to the Study Assessments and Procedures section of the protocol for detailed information on each procedure and assessment required for compliance with the protocol.

Visit Number	1	2	3	4
Visit Description	Vaccination 1	Follow-up Visit 1	Vaccination 2	Follow-up Visit 2
Visit Window (Days)	Day 1	28 to 42 Days After Visit 1	270 to 300 Days After Visit 1	28 to 42 Days After Visit 3
Obtain informed consent	Х			
Assign a participant number	Х			
Record demography, medical history, physical examination, vital signs	Х			
Record nonstudy vaccine information	Х	Х	X	Х
Record medication information ^a	Х	Х	X	Х
Review inclusion and exclusion criteria	Х			
Measure prevaccination temperature	Х		X	
Review temporary delay criteria	Х	Х	X	Х
Review continued eligibility		Х	X	Х
Obtain blood draw for immunogenicity assessment	Xb	Х	Xb	Х
	(~5mL)	(~5mL)	(~5mL)	(~5mL)
Administer investigational product ^e	Х		Х	
Observe and record acute reactions for 30 minutes after investigational product administration	Х		X	
Provide the parent(s)/legal guardian(s) with a contact card	Х			
Provide parent(s)/legal guardian(s) with an e-diary, thermometer, and measuring device and instruct to collect local reactions and systemic events until 7 days after vaccination ^d	X		X	
Review and/or collect e-diary (if applicable) ^e		Х		Х
Record and report AEs	X	X	X	Х

Table 4.Schedule of Activities (SoA)

PFIZER CONFIDENTIAL Page 13

Table 4.Schedule of Activities (SoA)

Visit Number	1	2	3	4
Visit Description	Vaccination 1	Follow-up Visit 1	Vaccination 2	Follow-up Visit 2
Visit Window (Days)	Day 1	28 to 42 Days	270 to 300 Days	28 to 42 Days
		After Visit 1	After Visit 1	After Visit 3
Record and report SAEs and NDCMCs ^f	X			X

a. Only concomitant medications used to treat SAEs and NDCMCs will be recorded.

b. Blood sample will be collected prior to vaccination.

c. Remind the participant's parent(s)/legal guardian(s) that the use of prophylactic antipyretic/pain medication, while permitted, is not recommended on the day of investigational product administration (before or after vaccination).

d. The participant's parent(s)/legal guardian(s) will record local reactions and systemic events in an e-diary for the 7 days following each dose of Nimenrix. Use of antipyretic/pain medications will also be collected daily in an e-diary for 7 days after vaccination. The participant's parent(s)/legal guardian(s) will be instructed to contact the study staff if the participant experiences redness or swelling >14 caliper units, severe pain at the injection site, or a fever >40.0°C or has an emergency room visit or hospitalization.

e. Designated site staff will review e-diary data online at frequent intervals (daily is optimal) for the 7 days following each dose of Nimenrix to evaluate participant compliance and as part of the ongoing safety review.

f. An NDCMC is defined as a disease or medical condition, not previously identified, that is expected to be persistent or otherwise long-lasting in its effects.

PFIZER CONFIDENTIAL Page 14

3. ENDPOINTS AND BASELINE VARIABLES: DEFINITIONS AND CONVENTIONS

3.1. Primary Endpoints

3.1.1. Primary Safety Endpoints

In participants receiving Dose 1 and Dose 2:

- Local reactions (redness, swelling, and pain at injection site) within 7 days after Dose 2.
- Systemic events (fever, decreased appetite, drowsiness, and irritability) within 7 days after Dose 2.
- Use of antipyretic medications within 7 days after Dose 2.
- AEs within 30 days after Dose 2.
- SAEs during the study within 30 days after Dose 2.
- NDCMCs during the study within 30 days after Dose 2.
- Immediate AEs after Dose 2.

3.1.2. Primary Immunogenicity Endpoints

In participants receiving both doses of Nimenrix and who are in compliance with the key protocol criteria (evaluable participants):

- rSBA titers for each of the MenA, MenC, MenW-135, and MenY serogroups at baseline, at 1 month after Dose 1, at Dose 2, and at 1 month after Dose 2 of Nimenrix.
 - Classification of titer as \geq 1:8 at each time point.

3.2. Secondary Endpoints

3.2.1. Secondary Safety Endpoints

In participants receiving at least 1 dose of study intervention:

- Local reactions (redness, swelling, and pain at injection site) within 7 days after Dose 1.
- Systemic events (fever, decreased appetite, drowsiness, and irritability) within 7 days after Dose 1.
- AEs within 30 days after Dose 1.
- SAEs during the study (within 30 days after Dose 1, from 1 month after Dose 1 through 9 months after Dose 1, and from Dose 1 through 9 months after Dose 1).

- NDCMCs during the study (within 30 days after Dose 1, from 1 month after Dose 1 through 9 months after Dose 1, and from Dose 1 through 9 months after Dose 1).
- Immediate AEs after Dose 1.

3.2.2. Secondary Immunogenicity Endpoints

In participants who have received the first dose of Nimenrix and who are in compliance with the key protocol criteria (evaluable participants):

- rSBA titer for each of the MenA, MenC, MenW-135, and MenY serogroups at baseline and at 1 month after Dose 1.
 - Classification of titer as $\geq 1:8$, $\geq 1:128$ at each time point.
- hSBA titer for each of the MenA, MenC, MenW-135, and MenY serogroups at baseline and at 1 month after Dose 1.
 - Classification of titer as $\geq 1:4$, $\geq 1:8$ at each time point.

In participants who have received the first and second dose of Nimenrix and who are in compliance with the key protocol criteria (evaluable participants):

- rSBA titer for each of the MenA, MenC, MenW-135, and MenY serogroups at baseline, at 1 month after Dose 1, at Dose 2, and at 1 month after Dose 2.
 - Classification of titer as $\geq 1:128$ at each time point.
- hSBA titer for each of the MenA, MenC, MenW-135, and MenY serogroups strains at baseline, at 1 month after Dose 1, at Dose 2, and at 1 month after Dose 2.
 - Classification of titer as $\geq 1:4$, $\geq 1:8$ at each time point.

At each visit where assay titers are available (Visits 1, 2, 3, and 4), participants with rSBA (or hSBA) titers \geq LLOQ will be derived as follows:

- = . , if the assay result is missing, indeterminate, or otherwise unavailable;
- = 1, if the assay result meets the specific LLOQ value;
- = 0, if the assay result does not meet the specific LLOQ value.

The threshold values for MenA, MenC, MenW-135, and MenY serogroups are:

- $\geq 1:8$ and $\geq 1:128$ for rSBA titers
- $\geq 1:4$ and $\geq 1:8$ for hSBA titers

3.3. Other Endpoint

3.3.1. Exploratory Safety Endpoints

In participants receiving any dose of study intervention:

- Local reactions (redness, swelling, and pain at injection site) within 7 days after any dose.
- Systemic events (fever, decreased appetite, drowsiness, and irritability) within 7 days after any dose.
- AEs within 30 days after any dose.
- SAEs within 30 days after any dose and throughout study (from Dose 1 through 1 month after Dose 2).
- NDCMCs within 30 days after any dose and throughout study (from Dose 1 through 1 month after Dose 2).

3.4. Baseline Variables

3.4.1. Demographic, Medical History, and Baseline Characteristic Variables

Demographic variables collected at each dose include sex (male or female), race, ethnicity, and date of birth. Race collected includes:

- Black or African American
- Asian
- White
- Not reported

Ethnicity collected includes:

- Hispanic or Latino
- Non-Hispanic/non-Latino
- Not reported

Age at each dose (in days) will be derived as (dose date – date of birth +1). For participants who were enrolled but not vaccinated, the consent date will be used in place of the date of Dose 1 for the Dose 1 age calculation.

In cases where more than 1 category is selected for race, the participant would be counted under the category "multiracial" for analysis.

PFIZER CONFIDENTIAL
Page 17

Medical history will be assessed at Visit 1 and categorized according to the current version of MedDRA (at the time of reporting).

The physical examination will be assessed prior to vaccination at Visit 1 and each body system examined will be recorded in the CRF as normal, abnormal, or not done.

3.5. Safety Endpoints

3.5.1. Adverse Events

The relationship between (S)AEs and the investigational products will be characterized as related or not related as determined by investigators and as described in the protocol. The severity of AEs will be characterized as mild, moderate, and severe.

The time period for actively eliciting and collecting (S)AEs and NDCMCs for each participant is outlined in Table 5.

Visit Window	Visits 1-2	Visit 3-4
(Days)	Day 1 Through 28 to 42 Days After	270 to 300 Days After Visit 1 Through 28 to
	Visit 1	42 Days After Visit 3
Nonserious AEs	ICD through and including Visit 2	From Visit 3 through and including Visit 4
	(1 month after Dose 1)	(1 month after Dose 2)
SAEs	ICD through the end of study	
NDCMCs	ICD through the end of study	
Immediate AEs	Within the first 30 minutes of each dose	

Table 5. Summary of Adverse Event Collection

Abbreviations: ICD = informed consent document; NDCMC = newly diagnosed chronic medical condition.

An NDCMC is defined as a disease or medical condition not previously identified that is expected to be persistent or otherwise long-lasting in its effects.

The time period for actively eliciting and collecting AEs ("active collection period") for each participant/parent(s)/legal guardian begins from the time the participant/parent(s)/legal guardian provides informed consent, which is obtained before the participant's participation in the study (ie, before undergoing any study-related procedure and/or receiving investigational product), through and including Visit 2, and from Visit 3 through including Visit 4. SAEs and NDCMCs will be categorized according to MedDRA terms. NDCMCs and SAEs will be collected from the signing of the ICD through the end of the study. For participants who are screen failures, the active collection period ends when screen failure status is determined.

Medical occurrences that begin before consent will be recorded on the Medical History/Current Medical Conditions section of the CRF, not the AE section.

All events collected on the CRF will be categorized according to the current version of MedDRA (at the time of reporting).

3.5.1.1. Analysis Intervals

There will be 6 analysis intervals for the AE data collected via the CRF (Table 6). The analysis populations used for these intervals are described in detail in Section 4.

#	Analysis Interval	Analysis Population	Interval Start Date (Inclusive)	Interval Stop Date (Inclusive)	Safety Data
1	Within 30 days after Dose 1	Dose 1 safety	Vax 1 date	Vax 1 date + 30 days	AEs, SAEs, NDCMCs
2	Within 30 days after Dose 2	Dose 2 safety	Vax 2 date	Vax 2 date + 30 days	AEs, SAEs, NDCMCs
3	Within 30 days after any dose	Safety	Vax 1 date or Vax 2 date	Vax 1 date + 30 days or Vax 2 date + 30 days	AEs, SAEs, NDCMCs
4	From 1 month after Dose 1 through 9 months after Dose 1	Dose 1 safety	Visit 2 date	Visit 3 date	SAEs, NDCMCs
5	From Dose 1 through 9 months after Dose 1	Dose 1 safety	Vax 1 date	Visit 3 date	SAEs, NDCMCs
6	Throughout study	Safety	Vax 1 date	Visit 4 date	SAEs, NDCMCs

 Table 6.
 Analysis Intervals for AEs, SAEs, and NDCMCs

Abbreviations: NDCMC – newly diagnosed chronic medical condition.

Two analysis intervals will be applied to immediate AEs (Table 7).

 Table 7.
 Analysis Intervals for Immediate AEs

#	Analysis Interval	Analysis Population	Interval Start Date/Time (Inclusive)	Interval Stop Date/Time (Inclusive)
1	Dose 1	Dose 1 safety	Vax 1 time	Vax 1 time + 30 minutes
2	Dose 2	Dose 2 safety	Vax 2 time	Vax 2 time + 30 minutes

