# 2.3.1. Risk Assessment

| Potential Risk of Clinical Significance   | Summary of Data/Rationale for Risk  | Mitigation Strategy   |  |  |  |  |  |
|---|---|---|--|--|--|--|--|
| Study Intervention(s) – Nimenrix  |   |   |  |  |  |  |  |
| The common risks associated with Nimenrix in infants categorized as very common or common adverse reactions include appetite loss, irritability, drowsiness, fever, swelling at injection site, tenderness at injection site, redness at injection site, diarrhea, vomiting, and rash; uncommon adverse reactions include crying, nausea, injection site hematoma, injection site induration, injection site pruritus, injection site warmth, and injection site anesthesia; and adverse reactions categorized with unknown frequency include extensive limb swelling at the injection site, frequently associated with erythema and sometimes involving the adjacent joint or swelling of the entire limb. | The risks are based on the known safety profile of Nimenrix in infants as presented in the Nimenrix SmPC. | Eligibility criteria have been selected to ensure that only appropriate healthy participants are included in the study (see Section 5).  Individuals with significant reactions after vaccination or AEs considered by the investigator to present increased risk to the participant if rechallenged or who develop exclusionary conditions during the conduct of the study will be excluded from interventions but may be followed for safety.                     |  |  |  |  |  |
|   | Study Procedures – Venipuncture   |   |  |  |  |  |  |
| There is a risk of bleeding, bruising, hematoma formation, and infection at the venipuncture site.  | Venipuncture is required to collect immunogenicity data from participants.                                | Only qualified nurses, physicians, nurse practitioners, physician's assistants, phlebotomists, or medical assistants certified or otherwise authorized to draw blood per the standards and procedures of the investigative site as allowed by institutional, local, and state guidance will be allowed to draw blood to minimize local complications.  The volume and frequency of blood sample collection during the study has been minimized as much as possible. |  |  |  |  |  |

Nimenrix® (Meningococcal Polysaccharide Groups A, C, W-135, and Y Tetanus Toxoid Conjugate Vaccine) Protocol C0921062 Final Protocol, 23 October 2020

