# **5.5.** Criteria for Temporarily Delaying Enrollment/Randomization/Study Intervention Administration

# 5.5.1. Temporary Delay Criteria

The following conditions are temporary or self-limiting and a participant may be vaccinated and/or have blood drawn in the study once the condition(s) has/have resolved and no other exclusion criteria are met. The prevaccination immunogenicity blood draw and vaccination should take place on the same day (Visit 1 and Visit 3).

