#### 8.2. Safety Assessments

A clinical assessment, including medical history and measurement of temperature as appropriate for the age of the child, according to routine local practice, will be performed on all participants prior to vaccination to determine participant eligibility and to establish a clinical baseline. Significant medical history and significant findings observed during physical examination (if performed) will be recorded in the medical history CRF. Temperature measurement prior to vaccination will be documented and recorded in the CRF.

The participant will be observed for 30 minutes after each vaccination and any reactions during the visit will be assessed and recorded as AEs. AEs occurring within the first 30 minutes after investigational product administration will be defined as immediate AEs. The time of onset will be recorded for any AE that occurs on the same day as investigational product administration.

E-diary events, including local reactions (redness, swelling, and pain at the injection site) and systemic events (fever, decreased appetite, drowsiness/increased sleep, and irritability) that occur within the 7 days following investigational product administration (Days 1 to 7, where Day 1 is the day of vaccination) are graded as described in Section 8.2.2. Furthermore, AEs, SAEs, and NDCMCs will be collected as defined in Section 10.3.

Planned time points for all safety assessments are provided in the SoA. Unscheduled clinical laboratory measurements may be obtained at any time during the study to assess any perceived safety issues.

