For reactions that continue into the next vaccination visit, the duration will be calculated in a segmented fashion. The reaction end date will be set to the day prior to the next vaccination and will have a new start date as the day of next vaccination. The duration will be calculated separately from the new start date to the date of resolution. Participants with reactions spanning multiple vaccination visits will be included in a footnote.

Participants with no reported reaction have no duration.

The onset day of each local reaction will be derived. The onset day is defined as the first day of reporting the reaction with any severity after vaccination.

In summary, the following variables will be derived for local reactions:

- 1. Each local reaction on each day (Days 1 to 7) after each vaccination.
- 2. Each local reaction on any day (Days 1 to 7) after each vaccination and any vaccination.
- 3. Any local reaction on any day (Days 1 to 7) after each vaccination and after any vaccination.
- 4. Maximum severity of each local reaction on any day (Days 1 to 7) after each vaccination and any vaccination.
- 5. Maximum duration of each local reaction after each vaccination.

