6.3.1.4. Serious Adverse Events and Newly Diagnosed Chronic Medical Conditions

- Analysis set: Safety. Refer to Section 4 for visit-specific populations.
- Analysis methodology: Descriptive summary statistics including associated Clopper-Pearson 95% CIs.
- Intercurrent events and missing data: Missing AE dates will be handled according to the Pfizer safety rules.

• For the group, the numbers and percentage of participants with SAEs and NDCMCs for the analysis interval of within 30 days after any vaccination and throughout the study defined in Table 6 will be summarized. The (n), %, and 95% CI may be presented for any event, for each SOC, and for each PT within each SOC.

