6.3.1.5. Adverse Event

- Analysis set: Safety. Refer to Section 4 for visit-specific populations.
- Analysis methodology: Descriptive summary statistics including associated Clopper-Pearson 95% CIs.
- Intercurrent events and missing data: Missing AE dates will be handled according to the Pfizer safety rules.
- For the group, the numbers of participants with AEs for the analysis interval of within 30 days after any dose and throughout the study defined in Table 6 will be summarized. The (n), %, and 95% CI may be presented for any event, for each SOC, and for each PT within each SOC.

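### SAP Table 6 counts Dose 2-day events as Dose 1 follow-up, and SAP 6.3.1.5 asks for a study-long AE summary that no interval supports (minor)

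*SAP*

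**What the plan says.** **Interval boundaries.** SAP 3.5.1.1, Table 6, defines six intervals by calendar date. The stop column is headed "Interval Stop Date (Inclusive", and the start dates are inclusive too. Row 4 runs from the Visit 2 date to the Visit 3 date. Row 5, labelled "From Dose 1 through 9 months after Dose 1", runs from the first vaccination date to the Visit 3 date. Both cover SAEs and NDCMCs in the Dose 1 safety population. Row 2, which serves the primary Dose 2 endpoints, starts on the second vaccination date. Protocol 5.5.1 makes these the same day: "The prevaccination immunogenicity blood draw and vaccination should take place on the same day (Visit 1 and Visit 3".

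**Related rules.** SAP Section 4 defines the Dose 1 safety population by safety information from Visit 1 up to a point before Visit 3. For reactions that run into the next vaccination visit, SAP 3.5.2.1 says: "The reaction end date will be set to the day prior to the next vaccination". SAP Table 7, for immediate AEs, uses clock time, and protocol 8.2 states: "The time of onset will be recorded for any AE that occurs on the same day as investigational product administration".

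**Study-long AEs.** SAP 6.3.1.5 summarizes "participants with AEs for the analysis interval of within 30 days after any dose and throughout the study defined in Table 6". Row 6 of Table 6, the whole-study interval, lists SAEs and NDCMCs only. SAP 2.1 and 3.3.1 restrict the exploratory AE endpoint to 30 days after a dose. Protocol 8.3.1 and SAP Table 5 collect nonserious AEs from consent to Visit 2 and from Visit 3 to Visit 4, not in between.

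**The concern.** (a) Rows 4 and 5 describe safety after one dose. Read literally, they admit an SAE or NDCMC that began after the second injection, so a secondary one-dose percentage can contain a two-dose event.

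(b) Rows 1, 2, 3, 5 and 6 start on a whole vaccination date. AEs are collected from consent and again from Visit 3, and blood is drawn before the injection. The protocol names the hazards of that draw: "There is a risk of bleeding, bruising, hematoma formation, and infection at the venipuncture site". An event with onset before the injection would therefore count as post-dose, including in row 2, which is primary. The SAP's only exclusion is for occurrences that begin before consent.

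(c) A study-long AE percentage would combine periods with and without collection of nonserious events, so it could not be interpreted. It also has no interval in the table to which SAP 6.3.1.5 refers.

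**Working it through.** The plan states no figure on this point. The check sets the passages side by side, counts days, and sizes one misassigned infant.

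**Inputs**
- Visit 2 is V2 = 28 to 42 days after Visit 1, and Visit 3 is V3 = 270 to 300 days after Visit 1 (protocol 1.3, SAP Table 2).
- Visit 4 is W = 28 to 42 days after Visit 3 (same sources).
- Planned enrolment is about 150 (protocol 9.2). Intervals are Clopper-Pearson (SAP 5.2.1).

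**(a) The shared day.** Counting both end dates:
- Row 4 length = V3 − V2 + 1, from 270 − 42 + 1 = 229 to 300 − 28 + 1 = 273 days.
- Row 5 length = V3 + 1, from 271 to 301 days.
- Each shares exactly one day with row 2 when Dose 2 is given at Visit 3. That is 1/273 to 1/229 = 0.37% to 0.44% of row 4, and 1/301 to 1/271 = 0.33% to 0.37% of row 5. The share is small, but the day is an injection day.

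**Effect of one misassigned infant, N = 150**
- 1/150 = 0.67 percentage points.
- 0/150: 0%, with upper limit 1 − 0.025^(1/150) = 2.43%.
- 1/150: 0.67%, with lower limit 1 − 0.975^(1/150) = 0.02%. The upper limit is the 0.975 quantile of Beta(2, 149), 3.66%.
- With an assumed smaller denominator of 130, the step is 1/130 = 0.77 points. The intervals are 0 to 2.80% for 0/130 and 0.02 to 4.21% for 1/130.

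The same step applies to (b) in row 2, with the Dose 2 safety population as denominator. The documents give no same-day event rates, so expected counts cannot be computed for (a) or (b).

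**(c) Days without planned collection of nonserious AEs, if protocol 8.3.1 governs.** The Visit 2 and Visit 3 days are themselves covered.
- Uncollected days = V3 − V2 − 1, from 270 − 42 − 1 = 227 to 300 − 28 − 1 = 271.
- Follow-up, counted inclusively from Visit 1 to Visit 4 = V3 + W + 1.
- Smallest share (V2 = 42, V3 = 270, W = 42): 227/313 = 72.5%.
- Largest share (V2 = 28, V3 = 300, W = 28): 271/329 = 82.4%.
- Collected days = (V2 + 1) + (W + 1), from 58 to 86.

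SAP 6.3.1.4 uses nearly the same phrase, "for the analysis interval of within 30 days after any vaccination and throughout the study defined in Table 6", for SAEs and NDCMCs. There it agrees with row 6, so the wording in 6.3.1.5 looks carried over.

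**The case against.** On (a), the protocol estimand itself runs through Visit 3, and Table 6 intervals overlap by design: row 5 contains row 1, and row 6 spans the study. This stands, so appearing in two rows is not in itself a fault. The narrow point survives: the estimand does not say that events after the second injection belong to one-dose follow-up, and the Dose 1 safety population is framed by information before Visit 3. That definition decides who is included, not which events count, so it shows a mismatch rather than a rule that overrides Table 6. A reader might infer that Table 6 breaks the SAP's own rule for reactions that cross a vaccination. It does not: that rule governs the duration of diary reactions and is only an analogy.

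On (b), whole-date starts are a common convention and can only overcount, so they hide no post-dose event. Acute illness within 48 hours already delays vaccination, and a blood-draw bruise first noted after the injection would count under either rule. All of this stands. Programming rules are kept in a separate document (SAP Section 2) and may use onset time, but the SAP text does not say so.

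On (c), no study-long AE interval exists to be programmed, the endpoint is exploratory, and its percentage display is optional. Deleting the phrase changes no result planned in Table 6. The 73% to 82% figure also depends on protocol 8.3.1, because protocol 8.11.3 tells sites at Visit 3 to ask about nonserious AEs since the previous visit.

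**Conclusion.** The point holds as a minor one. Under (a), the stated dates put a post-Dose 2 SAE or NDCMC on the Dose 2 day into two secondary Dose 1 percentages. Under (c), SAP 6.3.1.5 requests a summary that neither Table 6 nor the endpoint definitions support. Item (b) is a free improvement rather than an error.

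The size is about 0.67 percentage points per misassigned infant, taking the planned 150 as denominator and Dose 2 as given on the Visit 3 date. The shares in (c) assume that protocol 8.3.1 governs over 8.11.3.

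A reader might infer that the primary Dose 2 results are materially distorted. The documents do not support that. Item (a) leaves row 2 correct, (b) can only add events and probably few, and the study tests no hypothesis and has no decision rule.

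One slip is editorial only. The whole-study exploratory estimand in SAP 2.1 labels Dose 1 as Visit 2 and the month after Dose 2 as Visit 3, but its words agree with row 6. It should not be read as a different interval.

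**What to change.** In the SAP:
- **Table 6, rows 4 and 5:** end immediately before the Dose 2 injection, using the recorded onset time. If Dose 2 is not given, end at the Visit 3 date or last contact, whichever is earlier. This stays within the protocol estimand.
- **Table 6, rows 1, 2, 3, 5 and 6:** count a vaccination-day event as post-dose only if its onset is at or after the injection, and treat a missing onset time as post-dose.
- **SAP 6.3.1.5:** delete the request for AEs over the whole study. Keep it in 6.3.1.4.
- **SAP 2.1 (editorial):** relabel the whole-study estimand as Visit 1, 3 months of age, to Visit 4, 13 months of age.

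These are wording edits plus minor programming. They need no new data and no change to the protocol estimands, and they can be made before the single analysis at study completion (SAP 7.1).

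Separately, protocol 8.11.3 and 8.3.1 must be reconciled on nonserious AEs between Visits 2 and 3. That is a protocol edit and may need an amendment with IRB/EC review (protocol 10.1.1), which could be combined with any other amendment.
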